Cognitive Behavioral Therapy to

Increase CPAP Adherence in Veterans

with PTSD

Statistical Analysis Plan

NCT02641496

October 6, 2023

DATA ANALYTIC PLAN

Hypothesis 1. (Primary Outcome) Effect of CBT on CPAP usage. We hypothesize that the CBT-OSA group will use CPAP more hours per night on average than the Education group. An ANOVA will be used to compare performance on the primary measure (CPAP mask-on time, a continuous variable) by Group (CBT-OSA versus Education group) at the end of the 1-year RCT (Day 365) adjusting for baseline CPAP mask-on time values. The analyses will be an intention to treat design in which drop-outs after the baseline evaluation will not be replaced. Their last CPAP mask-on time score will be considered their final score. Potential covariates (e.g., AHI prior to treatment, daytime sleepiness) will be considered in the analysis. In a RCT, we assume that the groups will be apportioned relatively equally on relevant background variables such as age, but we will verify this by presenting descriptive statistics on such variables. We do not propose to enter all possible background variables as covariates into this analysis.

Hypothesis 2-4. (Secondary Outcomes) Effect of CBT on Self-reported Everyday Activities, Mood and Quality of Life, Cognitive Outcomes and PTSD. Secondary analyses will be conducted to compare performance between groups at Day 365 on relevant measures listed in Table 4 using the same statistical approach as Hypothesis 1.

Hypothesis 2. Effect of CBT on Self-reported Everyday Activities, Mood and Quality of Life. We hypothesize that after initiating CPAP treatment, Veterans in the CBT-OSA group will report more improvement in the ease of performing everyday activities compared to that reported by those in the Education group. An ANOVA will be used to compare performance on the FOSQ Total Score (continuous variable) by Group at Day 365. Potential covariates: sleep efficiency.

Hypothesis 3. Effect of CBT on Cognitive Outcomes. We hypothesize that the CBT-OSA group will have better cognitive outcomes than the Education group over time. An ANOVA will be used to compare performance on CVLT-II Delayed Recall Score (continuous variable) by Group at Day 365. Potential covariates: education.

Hypothesis 4. Effect of CBT on PTSD. We hypothesize that the CBT-OSA group will have fewer PTSD symptoms than the Education group over time. An ANOVA will be used to compare the PCL-5 Total Score (continuous variable) by Group at Day 365. Potential covariates: type of trauma, PTSD treatment, gender.

Other Secondary Analyses. Other secondary analyses will also examine Group effects at the cessation of the 4-week treatment (Day 21). Complementary analyses will be conducted using all available time points with mixed modeling and regression techniques, however, after extensive discussion with our statistical advisors, we felt that the easily interpretable ANOVA approach should be the primary statistical approach for this RCT.

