The reasons for low CPAP adherence include barriers related to discomfort in using CPAP and psychological barriers to behavior change [9]. A CBT treatment to improve CPAP adherence, CBT-OSA, has been successfully applied in civilian randomized controlled trials (RCTs) [10, 11]. Our VA intervention would involve delivery of CBT-OSA to PTSD Veterans to foster long-term CPAP adherence. The CBT-OSA treatment builds on the VISN 21 MIRECC's expertise in CBT interventions [e.g., VA rollout of CBT-Insomnia] as well as on our current research on PTSD Veterans with OSA. In this sample, the vast majority were not diagnosed with OSA prior to study entry; however, 69% of the participants had an AHI ≥ 10 [2]. Of the Veterans previously diagnosed with OSA, 63% were not using their CPAP. Specifically, this will be a 1-year parallelgroup RCT involving 120 PTSD Veterans with a diagnosis of OSA. All participants will receive treatment as usual in VA Pulmonary Service. Participants in the active arm will receive CBT-OSA from a trained Clinical Psychologist (CP). The other arm will receive individual participant education from an Educator (ED), but not CBT-OSA. Participants in both arms will receive weekly, individual sessions during the first 4 weeks of CPAP treatment and 3 booster sessions during the 1-year protocol. These two arms will be referred to hereafter as the CBT-OSA and the Education groups.

OBJECTIVES AND END POINTS

Objective 1. (Primary) Effect of CBT on CPAP usage. We hypothesize that the CBT-OSA group will use CPAP more hours per night on average than the Education Group. ANOVA will be used to test group differences over time in hours of "mask-on" CPAP usage per night. Primary endpoint: mean of Days 335-365.

Objective 2. (Secondary) Effect of CBT on Self-reported Everyday Activities, Mood and Quality of Life. We hypothesize that after initiating CPAP treatment, Veterans in the CBT-OSA group will report more improvement in the ease of performing everyday activities compared to that reported by those in the Education group. ANOVA will be used to test group differences over time in the total score on the Functional Outcomes of Sleep Questionnaire (FOSQ; [12], at Days 365 (endpoint).

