Objective 3. (Secondary) Effect of CBT on Cognitive Outcomes. We hypothesize that the CBT-OSA group will have better cognitive outcomes than the Education group over time. ANOVA will be applied to the California Verbal Learning Test, Delayed Free Recall Score with the primary endpoint at Day 365.

Objective 4. (Secondary) Effect of CBT on PTSD. We hypothesize that the CBT-OSA group will have fewer PTSD symptoms than the Education group over time. ANOVA will be used to

test group differences over time in the total score on the PTSD Checklist for DSM-5 (PCL-5), measured at Days 0, 21, 365. Primary endpoint is Day 365.

Table 1: Description of Measures

Table 1. Description	
Primary Outcome Measure:	
Hypothesis 1 Effect of CBT on CPAP adherence	
Objectively Measured CPAP Usage. The times when	The primary outcome measure is an objective
the mask is on the face are recorded and stored by the	measure: the average of CPAP mask-on time for
CPAP device ResScan™ data card.	the last 30 days of the 1-year RCT (Days 335-365).
Secondary Outcome Measures:	,
Hypothesis 2 Effect of CBT on Self-reported	
Everyday Activities, Mood and Quality of Life	
The Functional Outcomes of Sleep Questionnaire (FOSQ) [12] is a self-report measure of how much sleepiness impacts everyday activities and quality of life in multiple domains of function.	The FOSQ is designed to be given to individuals with a sleep disorder. In a 2011 VA clinical trial, FOSQ scores improved significantly in Veterans randomly allocated to APAP (n=105) and those allocated to CPAP (n=96), p's < .0001.
Hypothesis 3. Effect of CBT on Cognitive Outcomes.	
A cognitive battery known to be sensitive to OSA, and relevant to long-term CPAP adherence [9] will include our primary outcome measure, the California Verbal Learning Test [13], Long Delay Free Recall.	The purpose of the battery is to assess if changes in cognitive function occur, dependent on intervention group status. Baseline scores will also be used in supplementary data analyses on Moderators of treatment response to identify characteristics of patients who are best served by a CBT approach.
Hypothesis 4. Effect of CBT on PTSD.	
PTSD Checklist for DSM-5 (PCL-5) [14]. PCL-5 is a	The PCL-5 is designed to assess if the proposed
20-item self-report measure for PTSD based on DSM-5.	treatment has any effects on PTSD symptoms.

RESEARCH DESIGN AND METHODS PROCEDURES INVOLVING ELIGIBLE PARTICIPANTS

Study Timeline Schedule of Visits and Key Assessments

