The results of all of the screening assessments will be reviewed with Key Personnel. After consensus determination for study eligibility, the Study Coordinator will contact the participant to schedule a Baseline visit (if eligible), or provide appropriate referral and explanation (if deemed ineligible).

Enrollment, Randomization, and Baseline Measures

RCT Enrollment and Randomization. After the two-phase screening, eligible participants will be invited to participate and, if willing, scheduled to begin within 3 to 4 weeks of the completion of the screening visit. The Baseline visit and Session 1 (Day 0) will be carefully coordinated with Pulmonary staff for the participants who will receive their CPAP on the day of Session 1 (before the start of Session 1). All eligible participants will be randomized by the Data Manager to one of the two intervention arms: "CBT-OSA" or "Education" and notify the treating CP or ED, respectively.

Baseline Measures. The Coordinator will administer a cognitive battery

Adherence Intervention: CBT-OSA vs. Education

All CBT-OSA treatment will be done by a CBT-trained Clinical Psychologist and aimed at changing a participant's behaviors and cognitions related to CPAP use. These cognitive and behavioral interventions will be taught in the initial four weekly clinic sessions and reinforced in three booster sessions. To increase motivation and positive expectations, CBT-OSA will also include treatment goals relevant to the particular participant's condition.

The treating CP will work closely with the PI for clinical supervision and protocol adherence. The CP will learn the CBT-OSA intervention and will be practiced in achieving treatment fidelity. The CP will work with the participant individually (during certain sessions with the participant and bed partner).

The Education arm will focus on educational material (e.g., sleep health, sleep disorders, PTSD, cardiovascular health) over four weekly sessions and reinforced in three booster sessions. All participants will have equal opportunities for contact time with research staff. Participants will bring their CPAP to all sessions to use for exposure intervention (if in CBT-OSA) and to allow study staff to download CPAP data.

Pre-CPAP Intervention Phase

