On Day 0, prior to starting or reinitiating CPAP (Pre-CPAP Intervention Phase), the Veteran will complete the following self-report measures: FOSQ, ESS, PCL-5, BDI-II, SEMSA and WAI-SAT. Then, participants in both arms, will have one individual in-clinic session (Session 1-Day 0) with their assigned CP or ED.

MEASURES

Consented Veterans who have been determined eligible and are willing to enter the RCT will be administered the measures described in Table 1 above.

DATA ANALYTIC PLAN

Hypothesis 1. (Primary Outcome) Effect of CBT on CPAP usage. We hypothesize that the CBT-OSA group will use CPAP more hours per night on average than the Education group. An ANCOVA will be used to compare performance on the primary measure [(the average of CPAP mask-on time for the last 30 days of the 1-year RCT (Days 335-365); a continuous variable)] by Group (CBT-OSA versus Education). The analyses will be an intention to treat design using multiple imputation for missing data [19]. We will perform multiple regression analyses to identify potential covariates (e.g., AHI prior to treatmen1, daytime sleepiness) which will be considered in the analysis. In a RCT, we assume that the groups will be apportioned relatively equally on relevant background variables, but we will verify this by analyzing specific baseline

variables (e.g., gender, age, education). We do not propose to enter all possible background variables as covariates into this analysis; however, we will perform multiple regression analyses to identify significant covariates. We will then include those variables in the ANOVA as covariates.

Hypothesis 2-4. (Secondary Outcomes) Effect of CBT on Self-reported Everyday Activities, Mood and Quality of Life, Cognitive Outcomes and PTSD. Secondary analyses will be conducted to compare performance between groups at Day 365 on relevant measures listed in Table 4 using the same statistical approach as Hypothesis 1.

Hypothesis 2. Effect of CBT on Self-reported Everyday Activities, Mood and Quality of Life. We hypothesize that after initiating CPAP treatment, Veterans in the CBT-OSA group will report more improvement in the ease of performing everyday activities compared to that reported by those in the Education group. An ANOVA will be used to compare performance on the FOSQ Total Score (continuous variable) by Group at Day 365.

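### Does the SAP's Day 365 wording for CPAP mask-on time set a different primary endpoint from the protocol's mean over Days 335-365?

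*SAP*

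**What the plan says.** The SAP (Data Analytic Plan, Hypothesis 1) names "the primary measure (CPAP mask-on time, a continuous variable") and compares it between the groups "at the end of the 1-year RCT (Day 365"). It states no range of nights. The only reference to averaging is in the hypothesis, which concerns average nightly hours of use.

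The protocol gives the window three times:

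- Objectives and End Points, Objective 1: "Primary endpoint: mean of Days 335-365".
- Table 1, primary outcome measure: the average over "the last 30 days of the 1-year RCT (Days 335-365").
- Data Analytic Plan, Hypothesis 1: "the average of CPAP mask-on time for the last 30 days of the 1-year RCT (Days 335-365"), inside the sentence that specifies the group comparison.

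The protocol's Overview adds that the team has a particular interest in use over the final three months. The SAP is dated October 6, 2023 and the protocol April 30, 2024. Neither says which governs if they differ.

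**The concern.** The SAP is where a reader expects the primary variable to be fixed exactly, and here it is not. For a questionnaire or a memory test, a visit day identifies the score. Mask-on time is logged by the device night after night, so a day number alone does not say which nights enter the variable. Taken at its most literal, the SAP describes use on one night, whereas the protocol describes a mean over about a month.

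Two things would be at stake if the literal reading were applied. A single night carries all of a participant's night-to-night variation, so the comparison would lose precision. An unstated window on the primary outcome could also let the nights be chosen after the data had been seen.

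**Working it through.** The documents give no standard deviation, effect size, alpha or power, so there is no figure of the plan's to reproduce. The check is mainly a comparison of texts.

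**1. Does the SAP's wording exclude the protocol's window?** No. In the protocol's schedule of visits, Day 365 is the final booster visit. The SAP uses the same day for the FOSQ, CVLT-II and PCL-5, so it works there as a visit label. A mean over the nights leading up to that visit is an end-of-study value under that label. The hypothesis's reference to average nightly use points the same way, though not decisively, because it could also mean an average across participants. Nothing in the SAP calls for one night.

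**2. Would the data be at hand?** Yes. Participants bring their device to every session, in part "and to allow study staff to download CPAP data". Table 1 says the mask-on times are stored on the device's data card.

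**3. Is the window clear in the protocol?** All three formal statements give Days 335-365. The final three months in the Overview are described as an interest and are not labelled the primary endpoint. There is one slip. Counted inclusively, the window is 365 − 335 + 1 = 31 days, while Table 1 and the Data Analytic Plan say 30 (365 − 335 = 30).

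To size that slip, assume equal correlation ρ between nights and unit single-night variance. The variance of a k-night mean is then ρ + (1 − ρ)/k. At ρ = 0.3:

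- k = 30: 0.3 + 0.7/30 = 0.3233
- k = 31: 0.3 + 0.7/31 = 0.3226

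The SD ratio is √(0.3233/0.3226) ≈ 1.001, a difference of about 0.1%. It is smaller at higher ρ.

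**4. What would the literal reading cost?** This illustrates why the wording drew attention. Neither document proposes a one-night analysis. The inputs are 60 per arm (120 randomised 1:1, from the protocol's Overview) and, as assumptions, full follow-up, two-sided alpha 0.05, 80% power for the 31-night mean, the same mean difference on one night, and no covariate adjustment.

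- Standardised difference: d = (1.960 + 0.842) × √(2/60) = 0.511.
- SD of the 31-night mean relative to one night: R = √((1 + 30ρ)/31).
- Single-night power: Φ(d × R / √(2/60) − 1.960).

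| ρ (assumed) | R | Single-night power |
|---|---|---|
| 0.3 | 0.568 | 0.356 |
| 0.5 | 0.718 | 0.521 |
| 0.7 | 0.842 | 0.655 |
| 0.9 | 0.950 | 0.759 |

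The spread from 36% to 76% comes entirely from the assumed ρ. It shows that a one-night endpoint would be a poor choice. It does not show that the plan makes that choice.

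**The case for a change.** The strongest case for acting is that mask-on time is the one outcome for which a visit label is not enough, and it is the primary outcome. An analyst with only the SAP could not tell which nights to use. One who then opened the protocol would also meet the three-month interest in the Overview. The SAP's drop-out rule carries forward a last mask-on score without saying whether that is a night or a mean. The documents' dates do not formally settle precedence, and a clarification would cost only wording.

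Part of this stands. The SAP is incomplete on its own, and under its drop-out rule the carried-forward score has no stated window. The protocol plans multiple imputation instead of carrying a score forward; that disagreement is a separate matter from the averaging window.

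The rest does not carry the point further. Leaving a window unstated is different from stating another one. The remaining freedom to choose nights is small, because the protocol publicly names a single window as the primary endpoint and any other choice would be a visible departure. The later date does not give the protocol formal authority, but it does mean that the most recent analysis text contains the window. The SAP's pointer to a Table 4 settles nothing either way: it concerns the secondary outcomes, and that table is in neither document as supplied.

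**Conclusion.** No change to the plan is needed. The SAP omits a detail that the protocol states three times, and its wording is compatible with that detail. The two documents describe one endpoint, mean nightly mask-on time over Days 335-365, one of them less fully.

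The practical effect is nil so long as the analysis uses the protocol's window. The 30-versus-31-day count is a clerical slip worth about 0.1% in the SD of the mean at ρ = 0.3. The power loss shown for a single night does not count against the plan, because it belongs to an analysis that neither document sets out.

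This conclusion rests on two assumptions: that the analyst works with both documents, and that Day 365 in the SAP is the final-visit label it is in the protocol's schedule. The text supports the second but does not state it outright.

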	Consent	Screen	BL*	Pre- Intervention Phase		Early Intervention Phase			Booster Session Phase			Final Booster Session
Treatment Session				1	Start CPAP	2	3	4	5	6	7	8
Procedure Day		-28 to	-14	0		7	14	21	90	180	270	365
Consent	Χ	Χ*										
Med Hx review		X	Χ*									X
Blood Sample				Χ								
Self-reports		Х	X*					Х	Х	Χ	Χ	Х
Semi-structured Clinical Interview		Х	Χ*									Х
Cognitive Battery		Х	X*									Х
Self-Efficacy Measure for Sleep Apnea				Х				Х	X	X	Х	Х
Working Alliance Inventory SAT**				Х		Х	Х	Х	X	Χ	Х	Х
In-clinic treatment sessions				Х		Х	Х	Х	X	X	Х	Х
CPAP Usage (Measurement Periods)					× _				-	>		

^{*}If Baseline (BL) visit is needed, it will include the activities that were not completed during the screening visit

After Session 1 (Day 0), participants will be called by their CP or ED daily for one week to provide early and consistent intervention.

^{**}WAI modified to apply to Sleep Apnea Treatment (SAT).

OVERVIEW

Aims and Design of the Study. To test the efficacy of CBT-OSA in improving CPAP usage, the design will be a 2-arm RCT: 120 PTSD Veterans who are recently diagnosed with OSA and newly initiating CPAP will be allocated by 1:1 random assignment to either the 'CBT-OSA' group or the Education group. All Veterans will participate in usual care in VAPAHCS Pulmonary Service which is considered standard of care. During the 1-year study, the CBT-OSA arm will include seven individual, in-clinic intervention sessions with a CBT-trained Clinical Psychologist (CP): one session prior to starting CPAP (Session 1-Day 0), followed by three in-clinic sessions within the first four weeks of initiating CPAP (Session 2-Day 7; Session 3-Day 14; Session 4-Day 21) and 3 booster sessions (Session 5-Day 90; Session 6-Day 180; Session 7-Day 365). Education participants will receive equivalent amounts of contact with a trained Educator. All participants will receive the same CPAP devices and appropriate follow-up as usual care at the VAPAHCS.

To test the efficacy of CBT-OSA, the two groups will be compared for differences in average hrs/day of CPAP use. We are particularly interested in the difference between the groups in CPAP usage during the final 3 months of this 1-year study. Group differences in average hrs/day of CPAP use during Weeks 0-4 will be examined as a secondary outcome.

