To determine if CBT-OSA therapy translates to better participant functional outcomes than those in the Education group, each participant will be asked to fill out the Functional Outcomes of Sleep Questionnaire [FOSQ; 12] on 3 occasions: before the first and final weekly CBT-OSA treatment sessions (Day 0, 21) and before the final booster session (Day 365) after initiating CPAP treatment. Each participant will also undergo a cognitive battery on 2 occasions: at Baseline (BL; before initiating CPAP) and 1 year later (Day 365). The entire project is expected to take 4 years).

PARTICIPANTS

Veterans will be recruited from the VAPAHCS weekly 1 hour outpatient OSA Group Clinic. The majority of attendees are newly diagnosed with OSA by a Board Certified Sleep Medicine Physician. During the group appointment, Veterans receive education about OSA and treatment from a sleep medicine physician (using a PowerPoint presentation). A Q&A session follows the physician's presentation. At the conclusion of Q&A, Veterans will be introduced to the study. The study will be described as research that could help improve the participant's ability to use CPAP. Interested Veterans will participate in a confidential screen for eligibility within 4 weeks of starting CPAP. Veterans can choose to initiate or decline CPAP treatment. While participating in the proposed project, they will continue to have access to their usual care.

Inclusion and Exclusion Criteria

Overview. The inclusion/exclusion criteria are designed to select PTSD Veterans who have a diagnosis of mild to severe OSA. Patients with dementia or severe psychiatric illness will be excluded because they may be less likely to complete the study or follow the protocol procedures. Veterans with mild comorbid conditions will not be excluded because comorbidities are common in Veterans, and we want to obtain results that would be generalizable to typical VA PTSD patients.

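### The SAP carries a drop-out's last CPAP score forward in the primary test while the later protocol multiply imputes; nothing withdraws the SAP rule, and a carried score does not measure the Days 335-365 mean

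*SAP*

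**What the plan says.** **SAP, Data Analytic Plan, Hypothesis 1.** The primary test compares mask-on time between arms at Day 365, by intention to treat. It says that "drop-outs after the baseline evaluation will not be replaced", and then: "Their last CPAP mask-on time score will be considered their final score". It gives no averaging period for that last score and does not mention Days 335-365.

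**Protocol, Data Analytic Plan, Hypothesis 1.** The same comparison has a different rule: "The analyses will be an intention to treat design using multiple imputation for missing data". No imputation model is given. The primary measure is "the average of CPAP mask-on time for the last 30 days of the 1-year RCT (Days 335-365"). Objective 1 and Table 1 of the protocol name the same window.

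**Where the usage data come from.** Under Adherence Intervention, participants bring the device to sessions, where staff download the data. Under Aims and Design of the Study, Veterans "newly initiating CPAP will be allocated by 1:1 random assignment"; the Pre-CPAP Intervention Phase section allows that some are restarting. The Participants section adds that "Veterans can choose to initiate or decline CPAP treatment" and that, during the project, "they will continue to have access to their usual care".

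**Other outcomes.** Each document applies its Hypothesis 1 approach to Hypotheses 2-4. The SAP also plans mixed models on all time points, but only as complementary analyses.

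**The concern.** Two documents give two missing-data rules for one primary test. Neither refers to the other's rule, ranks the documents, or keeps one rule as a sensitivity analysis. Two analysts, each following one document, could report different primary estimates from the same data, and the choice could be made after the data are seen.

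The rules are also not equally suited to the endpoint. The question is how much CPAP is used at the end of one year. Carry-forward answers with use at whatever earlier time the participant was last downloaded, and gives that figure the weight of an observed value. If use changes over the year, and drop-out or change differs between arms, the group difference shifts.

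**Working it through.** **1. Age of a carried score.** Inputs: session days from the protocol's visit schedule, and Day 335 as the start of the window. Age = 335 minus the day of the last download.

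| Last download (day) | Days before the window opens |
|---|---|
| 7 | 328 |
| 14 | 321 |
| 21 | 314 |
| 90 | 245 |
| 180 | 155 |
| 270 | 65 |

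No scheduled download before Day 365 contains a night of the window. Day 270 appears only in the schedule table, where it is Session 7 and the "Final Booster Session" on Day 365 is Session 8. The text under Aims and Design puts Session 7 on Day 365 and has no Day 270. That is a separate inconsistency to be reconciled; on the text's schedule the shortest gap is 155 days.

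**2. Participants with no score.** The SAP rule covers anyone who leaves after the baseline evaluation. A participant new to CPAP who leaves before any download has no on-study score to carry.

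**3. Bias of carry-forward.** Let d be the drop-out share, O the mean of those observed, L the drop-outs' last recorded use and T their true use in Days 335-365. An arm's mean is (1-d)O + dL under carry-forward and (1-d)O + dT in truth, an error of d(L-T). For the unadjusted difference, CBT-OSA (C) minus Education (E):

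bias = dC(LC-TC) - dE(LE-TE)

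This can favour either arm or be nil.

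**4. Gap between the two rules.** With M the mean imputed value, carry-forward minus imputation is:

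gap = dC(LC-MC) - dE(LE-ME)

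The documents give none of these inputs, so the following values are assumed. Education is 4 h at last download and 3 h at one year (LE = 4, ME = 3). The CBT-OSA advantage grows from 0.5 to 1.3 h (LC = 4.5, MC = 4.3), stays at 1.3 h (5.3, 4.3) or fades from 1.3 to 0.5 h (5.3, 3.5).

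| Advantage | Drop-out C/E 20%/20% | 15%/30% | 30%/15% |
|---|---|---|---|
| Growing | -0.16 | -0.27 | -0.09 |
| Constant | 0 | -0.15 | +0.15 |
| Fading | +0.16 | -0.03 | +0.39 |

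Examples: growing, 15%/30%: 0.15 x 0.2 - 0.30 x 1.0 = -0.27 h. Constant, 20%/20%: 0.20 x 1.0 - 0.20 x 1.0 = 0. Fading, 30%/15%: 0.30 x 1.8 - 0.15 x 1.0 = +0.39 h. If the imputed means equal the truth (M = T), these gaps are also the bias of carry-forward.

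**5. Is imputation always nearer the truth?** Suppose every drop-out is really at 0 h (T = 0). The bias is then dC x LC - dE x LE for carry-forward and dC x MC - dE x ME for imputation. Over the same nine cases imputation is nearer in six, carry-forward in two, and one is a tie. For example, growing, 20%/20%: carry-forward 0.20 x 4.5 - 0.20 x 4 = +0.10 h; imputation 0.20 x 4.3 - 0.20 x 3 = +0.26 h.

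**6. Scale.** With 60 per arm (120 allocated 1:1), two-sided 0.05 and 80% power (both assumed), a two-sample t test detects 0.516 SD: 0.516 x 2 = 1.03 h at an assumed SD of 2 h, and 0.516 x 2.5 = 1.29 h at 2.5 h.

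**The case against.** The strongest reply is that the matter is already settled. The protocol's analysis section reads as a later revision of the SAP's, with the same headings and the same sentence on Hypotheses 2-4, and with imputation standing where carry-forward stood. That makes imputation the likely current intent, so a reader should not infer that the trial will necessarily be analysed by carry-forward. What remains is that the SAP is the dedicated analysis document, nothing withdraws its rule, and the protocol's replacement has no model.

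A second reply is that the card records use continuously, so a late return could supply nights in the window. That is true, but the SAP rule makes no provision for it. It is also fair that the Days 335-365 window is the protocol's and not the SAP's; the difference in time point is itself part of what must be reconciled.

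Four stronger readings are tempting and not supported:

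- **That carry-forward favours CBT-OSA.** The sign depends on drop-out and decline by arm, which the documents do not give.
- **That drop-outs use no CPAP, or that imputation is always closer.** Leaving the study is not leaving usual care, and step 5 shows that imputation can be the further of the two.
- **That the significance verdict would often flip.** Simulations of the nine cases (60 per arm, SD 2.5 h) gave disagreement in 8% to 34% of trials, and about 5% to 29% on a repeat. Much of that is noise near the threshold. Imputation rerun on the same data disagreed with itself in 2% to 6%. The case with a gap of exactly 0 still gave about 9%, and a no-effect case about 4%. No weight is placed on this range.
- **That the SAP carries FOSQ, CVLT and PCL-5 scores forward.** Its sentence names only mask-on time, so its reach to Hypotheses 2-4 is ambiguous.

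**Conclusion.** The SAP's carry-forward rule is wrong as written, and it conflicts with the later protocol. Three findings rest on the documents alone: the two rules differ, neither is withdrawn, and a score from any scheduled download before Day 365 contains no night of the endpoint window (65 to 328 days short, unless a card is returned late). The rule also gives no value for a new CPAP user who leaves before any download.

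The effect on the result cannot be sized from the documents. On the assumed inputs the two rules differ by -0.27 to +0.39 h/night, and by 0 where drop-out and decline match between arms. At the top that is about 30% of the 1.29 h detectable at an assumed SD of 2.5 h (0.39/1.29 = 0.30). Both sign and size would change with other assumptions.

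**What to change.** - Delete the carry-forward sentence from the SAP.
- In both documents, state that the primary endpoint is the Days 335-365 mean and that missing values of it are multiply imputed. Name the imputation model, with arm and recorded earlier usage in it. This model is a proposal, since the protocol gives none.
- Add a sensitivity analysis that sets unknown use to 0 or applies a range of reductions, because imputation under missing at random can overstate use.
- State that the same approach, and not carry-forward, applies to Hypotheses 2-4.
- Optional, for the sponsor to decide: score documented non-users as 0 h/night. This is a choice of estimand that neither document makes, and the contradiction can be resolved without it.

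The cost is wording in the SAP and protocol and modest analysis work.
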